12.7.11 Safety Evaluation

Subjects will be monitored for 28 days for adverse events (detailed in **Section 7.2.2**). Adverse events should be assessed in terms of their seriousness, duration, intensity, and relationship to the study product. All anticipated and unanticipated adverse events will be collected. Subjects will be able to contact the investigator at any time during the study if they note any change in their medical condition. The outcome of each adverse event will be observed and documented.

In the interim analysis, safety analysis, including adverse events (pre-specified infusion events, serious and non-serious adverse events) incidence and description will be run on ITT population. In the final analysis, safety analysis will be run on Safety population because the randomization has been unblinded.

The safety analysis will list all adverse events by individual patients, with their treatment (allocated or actual received), event seriousness, duration, intensity, and relationship to the study product, and outcome. Furthermore, the serious adverse events and non-serious adverse events will be summarized using patient counts and percentages by organ systems, as well as compared between two groups by Pearson's chi-square tests or Fisher exact test, as appropriate.

12.8 Adjustments for Stratification and SARS-CoV-2 Infection

Analyses of the outcomes will be adjusted for stratification variables (PaO₂/FiO₂ ratio [<150 mmHg or ≥ 150 mmHg] and trauma vs. non-trauma), APACHE III scores at baseline, and baseline measure, where P-value < 0.20 between treatment group.

To better understand the hMSC effects in patient with COVID-19 disease, the primary and secondary endpoints specified in Section 12.6 and 12.7 will also be summarized and conducted in separate linear mixed-effects regression models, in a fashion parallel to the analyses of the above main primary endpoint models, stratified or adjusted by the following binary variables of interest prior to randomization:

- SARS-CoV-2 infection status obtained from medical chart: yes or no
- COVID-19 as a cause of ARDS which is adjudicated by the study physicians: yes or no
- Viral antigen levels measured by NIH lab (PI: [name]): the value will be categorized by greater or less than median value
- Dexamethasone (or equivalent steroid therapy): yes or no
- Other immunomodulatory agents: yes or no
- Anticoagulation and antiplatelet treatments: yes or no
- MSC viability at the time of administration

Furthermore, the primary and secondary endpoints will be analyzed by latent class analysis (LCA) subphenotype using the same procedures described in previous studies (23-26) and adjusted for SARS-CoV-2 infection. In addition, we will test for an interaction between MSC therapy and the subphenotypes for the clinical outcomes.

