11.2 Statistical Methods for Primary and Secondary Endpoints

Descriptive summary statistics (e.g. means and standard deviations, or median with inter-quartile, as appropriate) will be used to summarize the primary and secondary endpoints by study treatment. The primary and secondary efficacy endpoints will also be analyzed using appropriate models.

The primary endpoint, change in the oxygenation index over time, will be compared between treatment conditions using a linear mixed-effects regression model. The model will be estimated using likelihood estimation which will allow the inclusion of all collected data, regardless of the number of assessments available for assessment. Terms in the model will include the two stratification variables, treatment condition (active or placebo), time of assessment, condition-by-time, recruitment site and a site-by-treatment interaction term. A test of the treatment condition will directly test the main research question. Covariates identified by preliminary analysis as potentially confounding due to baseline differences will be added to the model.

The data analysis plan for secondary efficacy and safety endpoints has been provided in the Statistical Analysis Plan.

The primary and secondary endpoints (including clinical and biological data) will be adjusted for COVID-19 infection as a cause of ARDS, which is adjudicated by the study physicians.

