12.6 Analysis for Primary Efficacy Endpoint

The primary endpoint is the changes in the oxygenation index from the baseline to the time-points at 6, 12, 18, 24, 30 and 36 hours after infusion of study product. The oxygenation index will only be calculated when the patient is still being ventilated with positive pressure. If patient is on pressure support, oxygenation index will be treated as missing because the mean airway pressure is not reliable.

Descriptive summary statistics (e.g. means and standard deviations, or median with inter-quartile, as appropriate) will be presented for the oxygenation index values, as well as the changes of oxygenation index from the baseline to each following timepoint by allocated group in modified ITT population.

The change of oxygenation index, by allocated treatment groups in modified ITT Population, will be compared using two linear mixed-effects regression models: unadjusted and adjusted model. Both models will be estimated using maximum likelihood estimation, which will allow the inclusion of all collected data, regardless of the number of assessments available for assessment. All models will include the stratification variables: $\text{PaO}_2/\text{FiO}_2$ ($< 150 \text{ mmHg}$ or $\geq 150 \text{ mmHg}$) and trauma status (trauma vs. non-trauma). Terms in the unadjusted linear mixed-effects regression model will include the two stratification variables, treatment condition (active or placebo), time of assessment (by hour), condition-by-time, recruitment site and a site-by-treatment interaction term. A test of the treatment condition will directly test the main research question. The adjusted linear mixed-effects regression model will include all the variables from the unadjusted model described above plus covariates identified by preliminary analysis as potentially confounding due to baseline differences ($p\text{-value} < 0.20$). The treatment effects may vary with ARDS severity ($\text{PaO}_2/\text{FiO}_2$) or by trauma status, thus the interaction terms will be also included. Both unadjusted and adjusted models will be presented with coefficient with 95% confidence intervals.

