12.7 Analyses for Secondary Efficacy Endpoints

12.7.1 Respiratory Physiology Endpoints

The secondary endpoints, such as acute lung injury score, pulmonary dead space and RALE score, expanded oxygenation index up to 7 days and the reduction in ventilator ratios, will be analyzed by linear mix-effects regression models using the modified ITT population, in a fashion parallel to the analyses of the primary endpoint of oxygenation index. Incidence of barotrauma will be analyzed by mixed-effects logistic regression models using the modified ITT population. Counted measures, such as ventilator free days, will be analyzed using zero-inflated negative binomial models in a parallel fashion as well. Achieving pressure support and second infection endpoint will be analyzed using a logistic regression model.

The acute lung injury score (LIS), pulmonary dead space, chest radiograph assessment of pulmonary edema (RALE score) at days 0, 1, 2, 3 and 7 (5 timepoints) will be summarized in modified ITT population by allocated group.

The reduction in ventilatory ratio at 6, 12, 18, 24, 36 hours from the baseline will be summarized in modified ITT population by allocated group.

The incidence of barotrauma will be categorized as yes or not on days 1, 2, 3 and 7, and summarized by patient counts and percentages. Evidence of barotrauma includes the following:

- Pneumothorax
- Bronchopleural fistula
- Tracheobronchial fistula;
- Pneumomediastinum
- Subcutaneous emphysema
- Pneumoatocoele

Ventilator free-days by 7, 14 and 28 days will be calculated as described in *Section 8.7*. They will be summarized as median and interquartile range by allocated group, separately.

Duration of assisted ventilation over 28 days will be calculated among survivors by day 28. It will be summarized as median and interquartile range.

Achieving pressure support ventilation equal to 5 cm H₂O with positive end-expiratory pressure (PEEP) equal to 5 cm H₂O for 2 hours will be categorized as yes or not, and summarized by patient counts and percentages.

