12.7.4 In-hospital mortality at 14, 28 and 60 days

In-hospital mortality at 60 days is defined as all death following the initiation of study product administration in any health care facility prior to discharge “home” until study day 60. Study subjects still in a health care facility at study day 61 are considered alive for this endpoint. This definition will also applied to in-hospital mortality at 14 days and 28 days.

At interim analyses hospital mortality to day 60 will be estimated using the Kaplan Meier estimate with patients who are discharged home considered as censored at day 61. At the final analyses where 60 day mortality will be known for everyone the binomial estimate will be used. In-hospital mortality will be summarized as patient counts and percentages by allocated groups, and compared by Pearson’s chi-square tests or Fisher exact tests, as appropriate.

At the final report, in hospital mortality at 28 days and 60 days will also be analyzed with a unadjusted Cox proportional hazard model and reported as hazard ratios (HRs) with 95% confidence intervals. Furthermore, a multivariate Cox proportional hazard model will be applied, by including the stratification variables ($\text{PaO}_2/\text{FiO}_2 < 150 \text{ mmHg}$ or $\geq 150 \text{ mmHg}$; trauma vs. non-trauma), and any baseline parameters that suggests the evidence of randomization imbalance between two groups.

In addition, as described in Section 7.1.2, we will use the levels of the baseline plasma biomarkers (IL-8, Protein C, and serum bicarbonate \pm vasopressor use at randomization) to classify patients as hyper- or hyper-inflammatory subphenotypes. Using latent class analysis (LCA), we will test the association between hyper-inflammatory group and an increased higher hospital mortality at 28 and 60 days in the modified ITT population.

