12.7.6 Ordinal Scale for Clinical Improvement (OSCI) at 7, 14 and 28 days

WHO Ordinal Scale for Clinical Improvement will be evaluated at baseline, 7, 14 and 28 days, as described in Section 8.6.

To investigate the effects of hMSCs treatment on clinical outcome as measured by the OSCI, a longitudinal mixed-effects proportional odds ratio model will be estimated and tested. Prior to final modeling, descriptive statistics of the response categories will be tallied. The assumption of proportionality will be tested and, if not met, a model relaxing that assumption will be used. (22)

Additionally, OSCI will be aggregate stratified by COVID-19 status and perform the modeling specified above by adjusting for COVID-status.

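### SAP 12.8 names only linear mixed-effects models for the COVID-19 and other adjusted or stratified analyses, although SAP 12.7 gives many of the same secondary endpoints logistic, count, Cox or ordinal models

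*SAP*

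**What the plan says.** SAP 12.8 covers the analyses meant to show how hMSC effects look in COVID-19 patients. It says "the primary and secondary endpoints specified in Section 12.6 and 12.7 will also be summarized and conducted in separate linear mixed-effects regression models", run "in a fashion parallel to the analyses of the above main primary endpoint models". Seven stratifying or adjusting variables follow: SARS-CoV-2 status, COVID-19 adjudicated as the cause of ARDS, viral antigen level, steroids, other immunomodulators, anticoagulant or antiplatelet treatment, and MSC viability at administration.

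The model being paralleled is in SAP 12.6, where change in oxygenation index (OI) "will be compared using two linear mixed-effects regression models: unadjusted and adjusted model". Its terms include time of assessment and condition-by-time.

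SAP 12.7 specifies the main analyses of the secondary endpoints. For example:

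- 12.7.1: "Incidence of barotrauma will be analyzed by mixed-effects logistic regression models using the modified ITT population".
- 12.7.1: "Achieving pressure support and second infection endpoint will be analyzed using a logistic regression model". Ventilator-free days get a zero-inflated negative binomial model.
- 12.7.4: "in hospital mortality at 28 days and 60 days will also be analyzed with a unadjusted Cox proportional hazard model", with a multivariable Cox model as well. These stand beside a comparison of proportions.
- 12.7.6: the ordinal scale (OSCI) gets a longitudinal mixed proportional-odds model, and the COVID analysis is to "perform the modeling specified above by adjusting for COVID-status".

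Protocol 11.2 requires the adjustment but names no model for it: "The primary and secondary endpoints (including clinical and biological data) will be adjusted for COVID-19 infection as a cause of ARDS".

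**The concern.** The COVID-adjusted results are not peripheral here. Protocol 3.1 says the vast majority of enrolled patients had COVID-19, and Protocol 4.2 says every objective will be analysed by COVID-19 or other etiology. SAP 12.8 is the general specification for that work.

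Followed as written, an infection endpoint would have an odds ratio as its main regression result and a difference in proportions as its COVID-adjusted result. A reader could not tell whether adjustment had changed the treatment effect or only the scale. Comparisons between strata are exposed too, because an effect that is constant on the hazard or odds scale is generally not constant as a difference in risk. If the analyst departs from 12.8 instead, the model is chosen without pre-specification.

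**Working it through.** The plan states no figure on this point, so the check is mainly a comparison of text, with two small calculations.

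**1. Main regression in SAP 12.7 against what 12.8 names**

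| Outcomes | Number | Regression in 12.7 | Named in 12.8 |
|---|---|---|---|
| Infections (four types) | 4 | Logistic | Linear mixed |
| Pressure support achieved | 1 | Logistic | Linear mixed |
| Barotrauma | 1 | Mixed logistic | Linear mixed |
| Ventilator-free days (7, 14, 28) | 3 | Zero-inflated negative binomial | Linear mixed |
| In-hospital mortality, days 28 and 60 | 2 | Cox, beside a comparison of proportions | Linear mixed |
| OSCI | 1 | Mixed proportional odds | Linear mixed |
| In-hospital mortality, day 14 | 1 | None (chi-square or Fisher) | Linear mixed |
| Thromboembolic events | 1 | None (chi-square or Fisher) | Linear mixed |
| Ventilation duration in survivors | 1 | None stated for it (median and IQR) | Linear mixed |
| Glasgow score at discharge | 1 | None (bivariate analysis) | Linear mixed |

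With a different regression model: 4 + 1 + 1 + 3 + 2 + 1 = 12. With none: 1 + 1 + 1 + 1 = 4. Total 16. The adverse-event comparisons in 12.7.11 (chi-square or Fisher) are not counted. Ventilation duration might be read into the count-data sentence of 12.7.1, but it is not named there.

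The linear model does suit OI, lung injury score, dead space, RALE, ventilatory ratio, non-pulmonary SOFA and the repeated biomarkers.

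**2. Terms that do not apply**

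Eight of the 16 have a single value per patient: four infections, thromboembolism, pressure support, ventilation duration and Glasgow score (4 + 1 + 1 + 1 + 1 = 8). Time and condition-by-time have no meaning for these. Mortality and ventilator-free days at three horizons are cumulative versions of one outcome, not fresh repeated measurements.

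A patient random intercept, if one is intended, also fails for single-value outcomes. With one record per patient the variance of an observation is V = σ²(patient) + σ²(residual), and only the sum enters the likelihood. In a simulated set of 120 patients (assumed mortality 30% on placebo, 25% on hMSC), the log-likelihood was −69.878 whether 1% or 99% of V was assigned to the patient. With a random effect for site only, the model fitted and returned a difference in risk.

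**3. Effect of the scale**

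Assume a constant hazard ratio of 0.7 in two strata with assumed control mortality p. Treated mortality is 1 − (1 − p)^0.7.

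- p = 40%: 1 − 0.60^0.7 = 30.1%, a difference of −9.9 points.
- p = 15%: 1 − 0.85^0.7 = 10.8%, a difference of −4.2 points.

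On the linear scale the effect looks more than twice as large in the first stratum (9.9 / 4.2 ≈ 2.4), with no difference in hazard ratio. The 40% and 15% are illustrative, not trial estimates.

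**4. Direct contradiction**

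For COVID-adjusted OSCI, 12.7.6 carries its proportional-odds model forward and 12.8 says linear. Both cannot be followed.

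**5. Cell viability**

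The post-thaw viability test in Protocol Appendix E (step H.3) is marked not applicable for placebo. SAP 12.8 nevertheless lists viability among binary, pre-randomization variables. It has no value in the placebo arm, so it cannot be an ordinary covariate or stratum in a treatment comparison.

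**The case against.** The other side has several fair points.

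- **Loose drafting.** SAP 12.7.1 also describes the ventilator-free-day count model as run in parallel fashion, so the authors may use that word for shared terms across model families. That explains how 12.8 came about, but 12.8 names the family, and it is linear.
- **The models can be fitted.** A reader might infer that the 12.8 analyses are impossible for these endpoints. The documents do not support that. SAP 12.6 states no random-effects structure, so the identifiability failure above holds only if a patient intercept is meant. Barotrauma, OSCI and ventilator-free days can be run through a linear model, and 12.7.4 expects 60-day mortality to be known for everyone at the final analysis.
- **Mortality is not only a hazard ratio.** A reader might also infer that the main mortality result is a hazard ratio that 12.8 would displace. In 12.7.4 the proportions come first, Cox is added for days 28 and 60, and day 14 has no Cox model. A risk difference agrees in scale with the proportions; the mismatch is with the Cox results.
- **Some non-linear COVID models exist.** Besides OSCI, 12.7.5 and 12.7.9 specify mortality models for the neutrophil-to-lymphocyte ratio and fibrinogen that include treatment assignment and are repeated in COVID-19 patients. They are prognostic in purpose and labelled as both logistic and Cox, so they only partly fill the gap.
- **Low stakes.** SAP 12.5 calls the secondary endpoints supportive and exploratory.

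These points limit the concern. They do not remove the conflict between 12.8 and 12.7.

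**Conclusion.** The concern holds as a specification error with consequences for scale, not as a failure of the analysis. Twelve listed outcomes have a regression model in 12.7 that 12.8 does not carry into the stratified and adjusted analyses. Four more have no regression model to carry, and OSCI has two incompatible instructions. The fault applies to the variables listed in 12.8. It does not reach that section's opening paragraph on stratification factors and APACHE III, or its latent-class paragraph, neither of which names a linear mixed model.

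The primary OI analysis, its power and alpha, and the continuous repeated endpoints are unaffected. The affected results are exploratory, but they are the ones readers will use to judge hMSC effects by COVID-19 status, so the correction should be made before unblinding. The text comparison needs no assumptions; the scale example rests on the assumed hazard ratio and control risks.

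**What to change.** In SAP 12.8:

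1. Replace the reference to separate linear mixed models with a rule that each endpoint keeps the regression model assigned to it in 12.6 or 12.7, with the listed variable added as a covariate or the model fitted within its levels.
2. State that 12.7.6 governs OSCI.
3. Name a model where 12.7 gives only a summary or bivariate test. Examples are logistic regression for day-14 mortality and thromboembolic events, linear regression on a suitable scale or a rank-based method for ventilation duration in survivors, and ordinal regression for the Glasgow score.
4. Remove MSC viability from the covariates and strata of the treatment comparisons, and analyse it within the cell arm.
5. Say whether 12.8 is meant to extend to the adverse-event comparisons in 12.7.11.

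The cost is a few SAP lines. Code for the 12 outcomes that already have a model is reused; the remaining four and the within-arm viability analysis need a little more. No new data or patients are required.

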4.2 Secondary Objectives

The secondary objectives of this study are to assess the potential efficacy of intravenous infusion of hMSCs in patients with ARDS including (1) an improvement in several physiologic and functional endpoints of respiratory failure, (2) a reduction in the incidence of secondary infections, (3) a reduction in systemic organ failure and in-hospital mortality, (4) improved neurocognitive function at hospital discharge, (5) incidence of thromboembolic events, as well as (6) to acquire mechanistic data regarding the activity of hMSCs in ARDS patients from biologic samples of plasma, urine and mBAL. In addition, safety will be monitored as defined by the incidence of pre-specified infusion associated events and of unexpected severe adverse events in ARDS patients treated with hMSCs. Because the vast majority of patients enrolled in this trial will have had ARDS secondary to COVID-19, all of the objectives will be analyzed according to whether the patient developed ARDS from COVID-19 or another etiology.

5 Study Design

This clinical study design is a randomized, double-blinded, placebo-controlled Phase 2b clinical trial using a 10×10^6 cell/kg dose of hMSCs. Subjects will be randomized in a 1:1 randomization scheme to receive hMSCs or cell reconstitution media (1:1 mix of 5% human serum albumin and 10% Dextran 40) as the placebo; the study will enroll 120 patients who achieve a stable clinical baseline and receive study product (either hMSCs or the placebo) as described in **Section 9.4**.

The DSMB will review adverse outcomes and protocol compliance. A pre-specified interim review will occur after 60 subjects have been enrolled and received study product; enrollment will continue during DSMB review. All pre-specified clinically important events and unexpected serious adverse events including death through day 28 from study product administration will be reported to the DSMB on an ongoing basis; the study will be stopped for a safety evaluation by the DSMB if they have any concerns or if three subjects have pre-specified clinically important events or unexpected serious adverse events EXCEPT death since death will be common in this critically ill population due the nature of the underlying illness (e.g., ARDS).

6 Endpoints

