10 SAMPLE SIZE DETERMINATION

The sample size for this trial will be 60 patients in the hMSCs arm and 60 patients in the placebo arm, for a total of 120 patients with a balanced randomization of patients with $\text{PaO}_2:\text{FiO}_2 < 150$ mmHg. This sample size was determined on the basis of feasibility.

Given the sample size of 60 per treatment condition, in this multisite, randomized trial using oxygenation index as the primary outcome and measures taken at 6 time points, it is estimated the study will have 80% power to detect a difference between conditions for an effect size as low as 0.43. Using the pilot data from Day 4, for example, this would translate to approximately a difference of 1.29 in the oxygenation index.

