12.5 General Methodology

Study Investigators, Study Coordinators, Data Manager and Statistician will be blinded to treatment assignment (randomization assignment will be coded as A group vs. B group) during the study prior to data lock.

Parameters ascribed to the safety and efficacy of patients will be summarized by modified ITT population defined in Section 11.

Continuous variables will be summarized using tables of descriptive statistics: number of patients with recorded observations, mean, standard deviation, median, minimum, maximum and interquartile range (IQR). Comparison of continuous parameters between two groups will be performed using T-test or Wilcoxon-Mann-Whitney test, as appropriate. Categorical variables will be summarized using counts and percentages, and compared between two groups using Pearson's chi-square or Fisher exact test, as appropriate. Based on the data shown in our previous Phase 2a

study, biomarker data will be summarized with descriptive statistics described above on original scale and log-transformed scale.

All statistical tests will be two-sided and will be performed at the 5% level of significance, unless otherwise stated. P-values will be rounded to three decimal places. P-values less than 0.001 will be reported as < 0.001 in tables. In bivariate analyses, P-values will not be adjusted for the comparisons of repeated outcomes between treatment allocations at multiple timepoints. Additional ad-hoc analyses may be conducted as deemed suitable.

As there is a single primary endpoint, and the secondary endpoints are to be used only in providing additional supportive exploratory information, there will be no adjustment for multiple testing.

All outputs will be produced using SAS and STATA (most up to date version available).

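### SAP 12.8 examines COVID-19 and concomitant-therapy groups by separate or adjusted models and names no treatment-by-variable interaction, so nothing in the plan estimates whether the treatment effect differs between them

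*SAP*

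**What the plan says.** Protocol 4.2 and SAP 4.2 make etiology a dimension of the whole trial: "all of the objectives will be analyzed according to whether the patient developed ARDS from COVID-19 or another etiology". Protocol 6.2.3 and SAP 7.2.3 put this into practice by running the endpoints separately within levels of SARS-CoV-2 status, viral antigen (split at the median), steroid therapy and other immunomodulators. SAP 12.8 plans separate mixed models, parallel to the primary model, that are "stratified or adjusted by the following binary variables of interest prior to randomization". Its list adds adjudicated COVID-19, anticoagulant and antiplatelet treatment, and MSC viability.

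No section names a treatment-by-COVID term, or a treatment-by-variable term for steroids, immunomodulators, antigen or anticoagulants. No section says how results from two strata are to be compared.

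Elsewhere the SAP does plan such terms. For the latent-class groups, 12.8 says "we will test for an interaction between MSC therapy and the subphenotypes for the clinical outcomes", and SAP 7.2.1 names the same test for the oxygenation index and 28-day mortality. SAP 12.6 adds treatment interactions with PaO2/FiO2 severity and trauma to the primary analysis, beside the site-by-treatment term.

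On testing, SAP 12.5 states: "All statistical tests will be two-sided and will be performed at the 5% level of significance, unless otherwise stated". It makes no multiplicity adjustment.

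**The concern.** When all objectives are split by etiology, readers will ask whether the cells work differently in COVID-19 and in other ARDS. A model fitted within each stratum gives two effects and two p-values but no estimate of their difference. A model adjusted for COVID-19 gives one pooled effect and assumes that the difference is zero. Neither option in SAP 12.8 therefore answers that question.

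Both documents say that by far the most enrolled patients had COVID-19, so the other stratum will be small. A significant result in the large stratum beside a non-significant one in the small stratum can arise from sample size alone, and could be reported as a COVID-specific effect. The omission concerns the factor that prompted the current protocol version (Protocol 3.1), while less central factors have an interaction planned.

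**Working it through.** **Inputs from the documents.** SAP 10: "60 patients in the hMSCs arm and 60 patients in the placebo arm, for a total of 120 patients"; "it is estimated the study will have 80% power to detect a difference between conditions for an effect size as low as 0.43"; "this would translate to approximately a difference of 1.29 in the oxygenation index" (implied SD 1.29/0.43 = 3.0); "measures taken at 6 time points". SAP 12.5: two-sided 5%. SAP 12.2: 1:1 allocation.

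**Assumptions.** The COVID-19 share is not given as a number, so 70%, 80% and 90% are used (36, 24 and 12 other patients of 120). Arms are taken as balanced within strata, with the same variance in both.

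**The plan's own figure.** For a single measurement the non-centrality is 0.43 × √(60/2) = 2.355, which gives 65.4% power, not 80%. With the mean of six measures the variance factor is (1 + 5ρ)/6, and 80% power needs a factor of 0.707, so ρ = (6 × 0.707 − 1)/5 ≈ 0.65. The documents give no ρ. The 80% is attainable but cannot be verified. It is used as stated, and 65% as a sensitivity case.

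**Stratum power.** Whole-trial non-centrality at 80% power is 1.96 + 0.84 = 2.80. With COVID share s it becomes 2.80√s in COVID patients and 2.80√(1−s) in the others. With stratum powers a and b, P(exactly one significant) = a(1−b) + b(1−a), and P(COVID only) = a(1−b).

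| COVID share | power, COVID | power, other | exactly one significant | COVID only |
|---|---|---|---|---|
| 70% | 65.0% | 33.5% | 54.9% | 43.2% |
| 80% | 70.7% | 24.0% | 60.8% | 53.7% |
| 90% | 75.7% | 14.4% | 68.3% | 64.9% |

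Example at 80%: 0.707 × 0.760 + 0.240 × 0.293 = 0.537 + 0.070 ≈ 0.608. Simulation of 40,000 trials with t-tests gave 54.9%, 61.1% and 68.7% for exactly one.

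**Sensitivity of exactly one significant, at shares of 70%, 80% and 90%.**
- Single-measurement power of 65%: 50%, 54%, 58%.
- Three quarters of the design effect: 45%, 48%, 51%.
- Half the design effect: 28%, 29%, 30%.
- No effect: 2 × 0.05 × 0.95 = 9.5%.

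**Interaction test on the same trials.** Under a common effect it rejects in 5% by construction (simulated 4.7% to 5.1%). Its standard error is that of the whole-trial effect divided by √(s(1−s)), so larger by a factor of 2.18, 2.50 and 3.33. The difference detectable with 80% power is 0.43 times that factor: 0.94, 1.08 and 1.43 SD, or 2.8, 3.2 and 4.3 oxygenation-index units. For a true difference of 0.43 the non-centrality is 2.80 divided by the factor (1.28, 1.12, 0.84), giving power of 25%, 20% and 13%.

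**The case against.** The strongest reply is that the plan never says it will compare p-values across strata. Its stated aim in SAP 7.2.3 is to understand effects in patients with COVID-19, which a within-stratum estimate with its confidence interval serves. This stands in part: the risk computed above arises only if someone reads the strata against each other. But the plan offers no other basis for comparison, and the objectives invite one.

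Second, SAP 12.8 models run parallel to the primary model, which already holds treatment interactions. That does not supply the missing term, because SAP 12.6 names effect-modifier terms only for PaO2/FiO2, trauma and site.

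Third, SAP 12.5 calls the secondary endpoints exploratory. The stratification in SAP 7.2.3 and 12.8 covers the primary endpoint too, and an exploratory subgroup statement still needs a contrast.

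Fourth, the interaction has low power, and six patient variables tested at 5% could give up to 1 − 0.95⁶ = 26% chance of at least one false signal if independent. Both points are correct and belong in the SAP. A wide interval shows openly that the trial cannot settle the question, which two separate p-values do not.

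A reader might infer that the SAP has no interaction tests outside the latent-class subphenotypes. SAP 12.6 contradicts that. The fault is inconsistency, not general neglect.

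**Conclusion.** The point holds: for COVID-19 status and the listed concomitant therapies, the planned methods do not estimate whether the treatment effect differs. At the design effect and an assumed 70% to 90% COVID share, exactly one stratum would be significant in about 55% to 68% of trials although the effect is the same in both.

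A reader might infer that a common effect will usually look like a COVID difference. The documents do not support that as a general statement. The share is assumed, the 80% power rests on an unstated correlation, and the frequency is about one half or less at three quarters of the design effect and under a third at half. Nor is every discordance the feared one, since the exactly-one figure includes trials in which only the non-COVID stratum is significant. The figures concern COVID-19 status alone. The documents give no prevalence for steroids, immunomodulators, antigen or anticoagulants, so for those the gap in method is shown but its size is not.

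**What to change.** In SAP 12.8, for adjudicated COVID-19 status first and then for the other listed pre-randomization patient variables, fit one model in all patients with a treatment-by-variable term. Report the interaction estimate, 95% CI and p-value as the only basis for any statement that effects differ, and give stratum effects as description. Say in advance what each adjusted model is for, since adjustment alone yields a pooled effect. Leave MSC viability out of this scheme: placebo contains no cells, so a treatment-by-viability term cannot be estimated. Align SAP 7.2.3 and Protocol 6.2.3.

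The cost is one term per model and no new data. The SAP should state the drawbacks: power of only about 13% to 25% for a difference of 0.43, several variables tested without multiplicity adjustment, and results to be labelled exploratory. A non-significant interaction must not be read as evidence of equal effects.
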